7.1.2.8 Tumor Tissue Collection

Tumor tissue will be evaluated as part of screening to determine if the sample is adequate for assessment of PD-L1 status (per inclusion 8 in Section 5.1.2).

Tumor tissue sample submitted in either formalin solution or FFPE block is acceptable. If submitting unstained cut slides from FFPE block, freshly cut slides must be received by the central laboratory within 14 days from when the slides are cut.

A fine needle aspirate (FNA) or cytologic specimen will not be acceptable. Tumor tissue should be submitted in the condition described in the procedure manual.

If the subject signs the Future Biomedical Research (FBR) consent, any leftover tissue that would ordinarily be discarded at the end of the main study will be retained for FBR. Details regarding time points for collection of tumor tissue are outlined in the Trial Flow Chart – Section 6.1.

Detailed instructions for tissue collection, processing and shipment are provided in the Procedures Manual.

7.1.2.9 Blood Collections – Genetics, Proteomics and Transcriptional Analyses

Details regarding time points for blood collection to support analysis of exploratory biomarkers presented in Section 4.2.3.3.1 are outlined in the Trial Flow Chart – Section 6.1.

Samples for planned, exploratory genetic analysis of DNA should be drawn unless there is a documented law or regulation prohibiting collection, or unless the IRB/IEC does not approve of the collection.

Detailed instructions for tissue collection, processing and shipment are provided in the Procedures Manual.

Any leftover specimens may be used for future biomedical research provided the subject has provided the relevant informed consent.

7.1.3 Laboratory Procedures/Assessments

Details regarding specific laboratory procedures/assessments to be performed in this trial are provided below. The total amount of blood/tissue to be drawn/collected over the course of the trial (from pre-trial to post-trial visits), including approximate blood/tissue volumes drawn/collected by visit and by sample type per subject can be found in the Procedures Manual.

7.1.3.1 Laboratory Safety Evaluations (Hematology, Chemistry and Urinalysis)

Laboratory tests for hematology, chemistry and urinalysis are specified in [Table 9](#).

Table 9 Laboratory Tests

Hematology	Chemistry	Urinalysis	Other
Hematocrit	Albumin	Blood	Serum β -human chorionic gonadotropin (β -hCG) ^a
Hemoglobin	Alkaline phosphatase	Glucose	PT (INR) ^d
Platelet Count	Alanine aminotransferase (ALT)	Protein	aPTT ^d
WBC (total and differential) ^f	Aspartate aminotransferase (AST)	Specific gravity	Total Triiodothyronine (T3) ^e
Red Blood Cell Count	Calcium	Microscopic exam, if abnormal results are noted	Free thyroxine (free T4)
Absolute Neutrophil Count ^f	Bicarbonate/carbon dioxide ^b	Urine pregnancy test ^a	Thyroid stimulating hormone (TSH)
Absolute Lymphocyte Count ^f	Carcinoembryonic antigen (CEA)		Blood for FBR
	Chloride		Blood for Proteomics
	Creatinine		Blood for Genetics
	Glucose		Blood for Transcriptional Analysis
	Phosphorus		
	Potassium		
	Sodium		
	Total Bilirubin		
	Direct Bilirubin, if total bilirubin is elevated above ULN		
	Total protein		
	Blood Urea Nitrogen		
	Uric acid		
	Urea ^c		

a Perform on women of childbearing potential only. Urine pregnancy test is preferred. If the urine test is positive or cannot be confirmed as negative, a serum pregnancy test will be required.

b. Test only if part of Standard of Care locally.

c Blood Urea Nitrogen is preferred; if not available, urea may be tested.

d Coagulation factors (PT/INR and aPTT) should be tested as part of the screening procedures for all subjects. Any subject receiving anticoagulant therapy should have coagulation factors monitored closely throughout the trial.

e Total T3 is preferred; if not available, free T3 may be tested locally. T3 and TSH may be tested centrally if testing is not available locally.

f. Absolute values or percentage per local laboratory.

Laboratory tests for screening should be performed within 3 days prior to the first dose of trial treatment. After Cycle 1, pre-dose laboratory procedures can be conducted up to 72 hours prior to dosing. Results must be reviewed by the investigator or qualified designee and found to be acceptable prior to each dose of trial treatment. For all subjects, unresolved abnormal labs resulting in drug-related AEs should be followed until resolution.

Chemistry labs will be collected on Day 1 of Cycles 2-6, then every 2 cycles for subjects in Cohort 1 and 3 (pembrolizumab monotherapy) and for subjects in Cohort 2 (Combination treatment) who are receiving only pembrolizumab (both chemotherapy agents were discontinued). For subjects in Cohort 2 who are receiving chemotherapy (with or without pembrolizumab), chemistry will be collected every cycle on Day 1.

Japan only - for subjects receiving capecitabine, chemistry should be collected as follows for Cycles 1 and 2: Cycle 1 - Days 8 and 15 (screening chemistry labs satisfy requirement for Day 1); Cycle 2 - Days 1, 8, and 15. After Cycle 2, chemistry labs will be collected every cycle on Day 1 as long as the subject is receiving treatment with either capecitabine and/or cisplatin.

CBC w/differentials will be collected on Day 1 of Cycles 2-6, then every 2 cycles for subjects in Cohort 1 and 3 (pembrolizumab monotherapy) and for subjects in Cohort 2 (Combination treatment) who are receiving only pembrolizumab (in the event both chemotherapy agents were discontinued). For subjects in Cohort 2 who are receiving chemotherapy (with or without pembrolizumab), CBC w/differentials will be collected every cycle on Day 1, 8 and 15 of Cycles 1-6 (screening CBC w/differentials labs satisfy requirement for Day 1 of Cycle 1); then on Day 1 of every cycle thereafter.

Please refer to the Trial Flow Chart (Section 6.1 and Section 6.2) for additional details regarding timing for laboratory tests.

7.1.3.2 Future Biomedical Research

The following specimens are to be obtained as part of Future Biomedical Research:

- Blood (DNA) for future use
- Leftover tumor tissue
- Leftover blood, plasma, and serum specimens (PK/ADA, blood samples for genetics, proteomics and transcriptional (RNA and DNA) analysis)

Details for collection and management as well as the use of specimens for Future Biomedical Research can be found in Appendix 12.2 and Appendix 12.3.

7.1.4 Other Procedures

7.1.4.1 Withdrawal/Discontinuation

When a subject discontinues/withdraws from participation in the trial, all applicable activities scheduled for the end-of-treatment visit should be performed at the time of discontinuation. Any adverse events which are present at the time of discontinuation/withdrawal should be followed in accordance with the safety requirements outlined in Section 7.2 - Assessing and Recording Adverse Events. Subjects who a) attain a CR or b) complete 35 administrations (approximately 2 years) of study treatment may discontinue treatment with the option of restarting treatment if they meet the criteria specified in Section 7.1.5.5. After discontinuing treatment following assessment of CR or 35 administrations of study treatment, these subjects should return to the site for a Safety Follow-up Visit (described in Section 7.1.5.4.1) and then proceed to the Follow-up Period of the study (described in Section 7.1.5.4.2).

7.1.4.1.1 Withdrawal From Future Biomedical Research

Subjects may withdraw their consent for Future Biomedical Research and have their specimens and all derivatives destroyed. Subjects may withdraw consent at any time by contacting the principal investigator for the main trial. If medical records for the main trial are still available, the investigator will contact the Sponsor using the designated mailbox ([contact]), and a form will be provided by the Sponsor to obtain appropriate information to complete specimen withdrawal. Subsequently, the subject's specimens will be removed from the biorepository and be destroyed. A letter will be sent from the Sponsor to the investigator confirming the destruction. It is the responsibility of the investigator to inform the subject of completion of destruction. Any analyses in progress at the time of request for destruction or already performed prior to the request being received by the Sponsor will continue to be used as part of the overall research trial data and results. No new analyses would be generated after the request is received.

In the event that the medical records for the main trial are no longer available (e.g., if the investigator is no longer required by regulatory authorities to retain the main trial records) or the specimens have been completely anonymized, there will no longer be a link between the subject's personal information and their specimens. In this situation, the request for specimen destruction cannot be processed.

7.1.4.2 Blinding/Unblinding

This is an open label trial; there is no blinding for this trial.

The study team will be blinded to PD-L1 expression status (positive or negative) for all subjects participating in the initial all-comers portion of Cohort 1 until the interim analysis of Cohort 1. Following the interim analysis, the Sponsor will be unblinded to PD-L1 data. Analyses or summaries of PD-L1 biomarker status will be limited and documented after the interim analysis. See additional details regarding blinding in Section 8.2.

7.1.4.3 Calibration of Equipment

The investigator or qualified designee has the responsibility to ensure that any device or instrument used for a clinical evaluation/test during a clinical study that provides information about inclusion/exclusion criteria and/or safety or efficacy parameters shall be suitably calibrated and/or maintained to ensure that the data obtained is reliable and/or reproducible. Documentation of equipment calibration must be retained as source documentation at the study site.

7.1.5 Visit Requirements

Visit requirements are outlined in Section 6.0 - Trial Flow Chart. Specific procedure-related details are provided above in Section 7.1 - Trial Procedures.

7.1.5.1 Screening

Approximately 28 days prior non-random assignment to one of 3 cohorts and study treatment, potential subjects will be evaluated to determine that they fulfill the entry requirements as set forth in Section 5.1. Screening procedures may be repeated after consultation with the Sponsor. Visit requirements are outlined in Section 6.0 – Trial Flow Chart.

Results of a test performed prior to the subject signing consent as part of routine clinical management are acceptable in lieu of a screening test if performed within the specified time frame. Screening procedures are to be completed within 28 days prior to the first dose of trial treatment except for the following:

- Laboratory tests and ECOG performance status are to be performed within 3 days prior to the first dose of trial treatment.
- For women of reproductive potential, a urine pregnancy test will be performed within 72 hours prior to the first dose of trial treatment.
- Biopsy collections may be collected up to 42 days prior to the first dose of trial treatment as presented in Sections 5.1.1 and 6.1.

Subjects may be rescreened after initially failing to meet the inclusion/exclusion criteria. Results from assessments performed during the initial screening period are acceptable in lieu of a repeat screening test if performed within the specified time frame and the inclusion/exclusion criteria is met.

7.1.5.2 Treatment Cycles

Visit requirements are outlined in Section 6.0 – Trial Flow Chart. Specific procedure-related details are provided above in Section 7.1 – Trial Procedures.

7.1.5.3 Discontinuation Visit

The Discontinuation Visit should occur at the time study treatment is discontinued for any reason. If the Discontinuation Visit occurs 30 days from the last dose of study treatment, at the time of the Safety Follow up Visit, procedures do not need to be repeated. Visit requirements are outlined in Section 6.0 – Trial Flow Chart. Specific procedure-related details are provided above in Section 7.1 – Trial Procedures. Additional details regarding subject withdrawal and discontinuation are presented in Section 5.8.

7.1.5.4 Post-Treatment

7.1.5.4.1 Safety Follow-up

The Safety Follow-Up Visit will be conducted approximately 30 days after the last dose of study treatment or before the initiation of a new anti-cancer treatment, whichever comes first.

Subjects who are eligible for retreatment with pembrolizumab (as described in Section 7.1.5.5) may have up to 2 safety follow-up visits, one after the Treatment Period and one after the Second Course Phase.

7.1.5.4.2 Follow-up Visits

Subjects who discontinue trial treatment for a reason other than disease progression will move into the Follow-Up Phase and should be assessed every 6 weeks (42 ± 7 days) by radiologic imaging to monitor disease status. After 1 year, the imaging time point will occur every 9 weeks (± 7 days). The Sponsor may request survival status to be assessed at additional time points during the course of the study (not to exceed approximately 12 weeks). Every effort should be made to collect information regarding disease status until the start of new anti-cancer therapy, disease progression, death, end of study or if the subject begins retreatment with pembrolizumab as detailed in Section 7.1.5.5. Information regarding post-study anti-cancer treatment will be collected if new treatment is initiated.

Subjects who are eligible to receive retreatment with pembrolizumab according to the criteria in Section 7.1.5.5 will move from the Follow-Up Phase to the Second Course Phase when they experience disease progression. Details are provided in Section 6.2 – Trial Flow Chart for retreatment with pembrolizumab.

7.1.5.4.3 Survival Follow-up

Once a subject experiences confirmed disease progression or starts a new anti-cancer therapy, the subject moves into the Survival Follow-Up Phase and should be contacted by telephone approximately every 12 weeks to assess for survival status until death, explicit withdrawal of consent for survival follow up, or the end of the study, whichever occurs first. Information regarding post-study anti-cancer treatment will be collected if new treatment is initiated.

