5.2.1.2.3 Dose Modification for Pembrolizumab

Dose modification and toxicity management for immune-related AEs associated with pembrolizumab

Adverse events associated with pembrolizumab exposure may represent an immunologic etiology. These immune-related AEs (irAEs) may occur shortly after the first dose or several months after the last dose of pembrolizumab treatment and may affect more than one body system simultaneously. Therefore, early recognition and initiation of treatment is critical to reduce complications. Based on existing clinical trial data, most irAEs were reversible and could be managed with interruptions of pembrolizumab, administration of corticosteroids, and/or other supportive care. For suspected irAEs, ensure adequate evaluation to confirm etiology or exclude other causes. Additional procedures or tests such as bronchoscopy, endoscopy, or skin biopsy may be included as part of the evaluation. Based on the severity of irAEs, withhold or permanently discontinue pembrolizumab and administer corticosteroids. Dose modification and toxicity management guidelines for irAEs associated with pembrolizumab are provided in [Table 4](#).

Table 4 Dose Modification and Toxicity Management Guidelines for Immune-related AEs Associated with Pembrolizumab

General instructions:				

 1. Corticosteroid taper should be initiated upon AE improving to Grade 1 or less and continue to taper over at least 4 weeks. 2. For situations where pembrolizumab has been withheld, pembrolizumab can be resumed after AE has been reduced to Grade 1 or 0 and corticosteroid has been tapered. Pembrolizumab should be permanently discontinued if AE does not resolve within 12 weeks of last dose or corticosteroids cannot be reduced to ≤ 10 mg prednisone or equivalent per day within 12 weeks. 3. For severe and life-threatening irAEs, IV corticosteroid should be initiated first followed by oral steroid. Other immunosuppressive treatment should be initiated if irAEs cannot be controlled by corticosteroids. 				
Immune-related AEs	Toxicity grade or conditions (CTCAEv4.0)	Action taken to pembrolizumab	irAE management with corticosteroid and/or other therapies	Monitor and follow-up

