6.0 TRIAL FLOW CHART

6.1 Initial Treatment Phase

Trial Period:	Screening	Treatment Cycles ^a (3 weeks per cycle)						End of Treatment (last dose) or Discontinuation	Post-Treatment		
		To be repeated beyond 6 cycles							Safety Follow-up (30 days from last dose)	Follow Up Visits ^b	Survival Follow-up ^f (Phone)
Treatment Cycle/Title:	Visit 1	1	2	3	4	5	6				
Scheduling Window (Days):	-28 to -1		± 3	± 3	± 3	± 3	± 3		± 7	± 7	± 7
Informed Consent	X										
Informed Consent for FBR ^c	X										
Inclusion/Exclusion Criteria	X										
Subject Identification Card	X										
Demographics and Medical History	X										
Prior and Concomitant Medication Review	X	X	X	X	X	X	X	X	X		
Clinical Procedures/Assessments											
Review Adverse Events	X	X	X	X	X	X	X	X	X	X	
12-Lead ECG (Local)	X										
Full Physical Examination	X							X			
Directed Physical Examination		X	X	X	X	X	X				
Ht (V1 only), Wt, & Vital Signs (T/P/RR/BP)	X	X	X	X	X	X	X	X			
ECOG Performance Status	X ^q		X	X	X	X	X	X			
Trial Treatment Administration ^p		X	X	X	X	X	X				
Post-study Anticancer Therapy Status										X	Q12W
Survival Status ^r		←----->									Q12W
LOCAL Laboratory Assessments											
Pregnancy Test – Urine or Serum β-HCG ^d	X										
PT/INR and aPTT ^e	X										
Chemistry Panel ^{e, f}	X		X	X	X	X	X ^f	X	X		
CBC with Differential ^{e, g}	X		X	X	X	X	X ^g	X	X		
T3, FT4, and TSH ^{e, h}	X		X		X		X, then Q2 cycles		X		
Serum carcinoembryonic antigen (CEA) ^{e, i}	X			X		X	X	X			
Urinalysis ^e	X										
CENTRAL Laboratory Assessments											
Blood for Future Biomedical Research ^c		X									
Blood for Proteomics and Genetics ^k		X									
Blood for RNA and DNA Analysis ^k		X	X	X				X			

Trial Period:	Screening	Treatment Cycles ^a (3 weeks per cycle)						End of Treatment (last dose) or Discontinuation	Post-Treatment		
		To be repeated beyond 6 cycles							Safety Follow-up (30 days from last dose)	Follow Up Visits ^b	Survival Follow-up ^f (Phone)
Treatment Cycle/Title:	Visit 1	1	2	3	4	5	6				
Scheduling Window (Days):	-28 to -1		± 3	± 3	± 3	± 3	± 3		± 7	± 7	± 7
Efficacy Measurements											
Tumor Imaging	X ^l				X ^m		X ^m	X ⁿ		X ⁿ	
Tumor Tissue Collection ^o	X	optional biopsy (close to dosing after 9 weeks of treatment)						X ^{optional}			

a. Unless otherwise specified, assessments/procedures are to be performed prior to dose administration on Day 1 of each cycle.

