7.1.1.5.2 Concomitant Medications

The investigator or qualified designee will record medication, if any, taken by the subject during the trial beginning at Treatment Cycle 1 through the Safety Follow-Up Visit for the Initial Treatment Phase. All medications related to reportable SAEs and ECIs should be recorded as defined in Section 7.2.

During the Second Course Phase, new medications started during the trial through the Safety Follow-Up visit should be recorded. Record all medications taken for SAEs as defined in Section 7.2.

7.1.1.5.2.1 Subsequent Anti-cancer Therapy Status

The investigator or qualified designee will review all new anti-cancer therapy initiated after the last dose of trial treatment. If a subject initiates a new anti-cancer therapy within 30 days after the last dose of trial treatment, the 30 day Safety Follow-up visit must occur before the first dose of the new therapy. Once new anti-cancer therapy has been initiated the subject will move into survival follow-up.

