7.2.3 Immediate Reporting of Adverse Events to the Sponsor

7.2.3.1 Serious Adverse Events

A serious adverse event is any adverse event occurring at any dose or during any use of Sponsor's product that:

- Results in death;
- Is life threatening;
- Results in persistent or significant disability/incapacity;
- Results in or prolongs an existing inpatient hospitalization;
- Is a congenital anomaly/birth defect;
- Is an other important medical event

Note: In addition to the above criteria, adverse events meeting either of the below criteria, although not serious per ICH definition, are reportable to the Sponsor in the same timeframe as SAEs to meet certain local requirements. Therefore, these events are considered serious by the Sponsor for collection purposes.

- Is a new cancer (that is not a condition of the study);
- Is associated with an overdose.

Refer to [Table 10](#) for additional details regarding each of the above criteria.

For the time period beginning when the consent form is signed until randomization/treatment allocation, any serious adverse event, or follow up to a serious adverse event, including death due to any cause other than progression of the cancer under study (reference Section 7.2.3.3 for additional details), that occurs to any subject must be reported within 24 hours to the Sponsor if it causes the subject to be excluded from the trial, or is the result of a protocol-specified intervention, including but not limited to washout or discontinuation of usual therapy, diet, placebo treatment or a procedure.

For the time period beginning at randomization/treatment allocation through 90 days following cessation of treatment, or 30 days following cessation of treatment if the subject initiates new anticancer therapy, whichever is earlier, any serious adverse event, or follow up to a serious adverse event, including death due to any cause other than progression of the cancer under study (reference Section 7.2.3.3 for additional details), whether or not related to the Sponsor's product, must be reported within 24 hours to the Sponsor either by electronic media or paper. Electronic reporting procedures can be found in the EDC data entry guidelines. Paper reporting procedures can be found in the Investigator Trial File Binder (or equivalent)

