7.2.3.2 Events of Clinical Interest

Selected non-serious and serious adverse events are also known as Events of Clinical Interest (ECI) and must be reported to the Sponsor.

For the time period beginning when the consent form is signed until randomization/treatment allocation, any ECI, or follow up to an ECI, that occurs to any subject must be reported within 24 hours to the Sponsor if it causes the subject to be excluded from the trial, or is the result of a protocol-specified intervention, including but not limited to washout or discontinuation of usual therapy, diet, placebo treatment or a procedure.

For the time period beginning at randomization/treatment allocation through 90 days following cessation of treatment, or 30 days following cessation of treatment if the subject initiates new anticancer therapy, whichever is earlier, any ECI, or follow up to an ECI, whether or not related to the Sponsor's product, must be reported within 24 hours to the Sponsor, either by electronic media or paper. Electronic reporting procedures can be found in the EDC data entry guidelines. Paper reporting procedures can be found in the Investigator Trial File Binder (or equivalent).

Events of clinical interest for this trial include:

1. an overdose of Sponsor's product, as defined in Section 7.2.1 - Definition of an Overdose for This Protocol and Reporting of Overdose to the Sponsor, that is not associated with clinical symptoms or abnormal laboratory results.
2. an elevated AST or ALT lab value that is greater than or equal to 3X the upper limit of normal and an elevated total bilirubin lab value that is greater than or equal to 2X the upper limit of normal and, at the same time, an alkaline phosphatase lab value that is less than 2X the upper limit of normal, as determined by way of protocol-specified laboratory testing or unscheduled laboratory testing.*

*Note: These criteria are based upon available regulatory guidance documents. The purpose of the criteria is to specify a threshold of abnormal hepatic tests that may require an additional evaluation for an underlying etiology. The trial site guidance for assessment and follow up of these criteria can be found in the Investigator Trial File Binder (or equivalent).

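### After progression without new anticancer therapy, no scheduled contact asks about adverse events between the day-30 safety visit and the day-90 end of SAE/ECI collection

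*Combined protocol and SAP*

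**What the plan says.** **Collection window.** Section 7.2.3.1 requires SAEs to be reported "through 90 days following cessation of treatment, or 30 days following cessation of treatment if the subject initiates new anticancer therapy, whichever is earlier". The first statement of the ECI window, in section 7.2.3.2, has the same limits: "30 days following cessation of treatment if the subject initiates new anticancer therapy, whichever is earlier, any ECI, or follow up to an ECI". A later paragraph of section 7.2.3.2 ends the ECI window 30 days after new therapy starts, not 30 days after study treatment stops.

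**Safety visit.** The Trial Summary and section 7.1.5.4.1 give all subjects a visit about 30 days after the last dose, or before new therapy if that is earlier. The flow charts allow ±7 days.

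**Scheduled review.** Section 7.1.2.1 ties adverse event assessment to the flow chart, with more frequent assessment if clinically indicated. In charts 6.1 and 6.2 the row "Review Adverse Events" is marked through End of Treatment, the safety visit and the Follow Up Visits. It is blank under Survival Follow-up.

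**Who gets which follow-up.** Section 7.1.5.4.2: "Subjects who discontinue trial treatment for a reason other than disease progression will move into the Follow-Up Phase", with visits every 6 weeks (every 9 weeks after the first year). After confirmed progression or new therapy, section 7.1.5.4.3 applies: "the subject moves into the Survival Follow-Up Phase and should be contacted by telephone approximately every 12 weeks to assess for survival status". Those calls also record post-study therapy. Section 7.1.1.5.2.1 adds: "Once new anti-cancer therapy has been initiated the subject will move into survival follow-up".

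**The concern.** The plan sets one collection window but schedules the asking differently according to why the subject stopped. A subject who stops without progression is seen repeatedly, with adverse events reviewed each time. A subject who progresses and starts nothing new is asked at about day 30 and then not again by schedule, although the window runs to day 90.

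Safety and tolerability is a primary objective in all three cohorts (section 3.1), and the protocol expects late events: "These immune-related AEs (irAEs) may occur shortly after the first dose or several months after the last dose of pembrolizumab treatment". The planned safety summary is counts and percentages of adverse events (section 8.6.2). An SAE treated at another hospital on day 60 enters that count only if someone tells the site. Late SAEs in progressors are therefore more likely to be missed than the same events in subjects who stop for other reasons, which pushes the reported counts down.

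**Working it through.** The plan states no figure to reproduce. The check counts days in the window after the last scheduled contact that includes adverse event review.

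**Inputs.** Window end: day 90, or day 30 with new therapy (7.2.3.1; first statement in 7.2.3.2). Safety visit: day 30 ±7, so day 23 to 37 (chart 6.1). Survival calls: every 12 weeks = 84 days, ±7 (7.1.5.4.3 and chart 6.1). Follow-up visits: every 6 weeks = 42 days in the first year (7.1.5.4.2). Day 0 is the last dose, taken as the day treatment ceases.

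**1. Stops for confirmed progression, no new therapy.** Days without scheduled review = 90 − day of safety visit.
- Visit on day 23: 90 − 23 = 67 days (67/90 = 74.4%)
- Visit on day 30: 90 − 30 = 60 days (66.7%)
- Visit on day 37: 90 − 37 = 53 days (58.9%)

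**2. Does the first survival call fall inside the window?** Section 7.1.5.4.3 gives no starting point for the 12 weeks.
- Counted from the last dose: 84 ± 7 = day 77 to 91
- Counted from a day-30 visit: 30 + 84 ± 7 = day 107 to 121, after the window has closed

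Neither call has an adverse event item.

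**3. Progresses in follow-up before day 90, no new therapy.** The remainder is 90 − day of last review. As an illustration, a last review on day 42 leaves 48 days.

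**4. Stops for another reason.** If the 6-week interval is counted from the last dose, reviews fall at about days 30, 42 and 84, and visits continue past day 90. There is no comparable gap.

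**5. Starts new therapy.** Under 7.2.3.1 and the first ECI statement the window closes at day 30. If therapy starts on day d before day 30, the safety visit must come first. With the visit taken at day d, the gap is 30 − d.
- d = 7: 23 days
- d = 14: 16 days
- d = 21: 9 days
- Start on or after day 30, visit on day 30: 0 days

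**6. ECIs under the later paragraph of 7.2.3.2.** The window closes at the earlier of day 90 and d + 30.
- d ≤ 30, visit at day d: 30 days without review
- d = 45, visit on day 30: 75 − 30 = 45 days
- d ≥ 60, visit on day 30: 90 − 30 = 60 days

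The two ECI statements therefore give gaps of 0 and 60 days for the same subject who starts new therapy on day 60.

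**The case against.** The strongest reply is that collection does not stop. Sections 7.2.3.1 and 7.2.3.2 oblige the investigator to report any SAE or ECI in the window within 24 hours, related or not. Related SAEs are reportable at any time. Section 7.1.2.1 allows extra assessment when clinically indicated, and survival calls detect deaths. This stands as far as it goes: ascertainment is passive, not absent. But a duty to report known events quickly does not make an unknown event known.

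Second, the ECI half is weaker than the SAE half. Section 7.2.3.2 lists only overdose and a laboratory-defined liver pattern. A telephone question cannot find the liver pattern, and chart 6.1 schedules no chemistry at the Follow Up Visits either. This stands, so the gain is mainly in SAEs. One qualification is that section 3.4.2 of the supplemental SAP still describes immune-related events as ECIs.

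Third, the safety analysis is descriptive, with no planned late-event rate and no comparison by reason for stopping. This also stands. The harm is under-counting in a primary safety summary, not distortion of a specified comparison.

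Fourth, section 7.1.5.4.3 requires confirmed progression, and chart 6.1 continues disease monitoring for subjects who stop without it. The gap is limited accordingly.

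A reader might also infer more than the documents support:
- **That progressors go straight to telephone calls.** They do not, because all subjects have the safety visit.
- **That subjects on new therapy lose most of a 90-day window.** Under 7.2.3.1 their window ends at day 30. Only the later ECI paragraph gives them a longer one.
- **That this is the largest group of subjects.** No count by reason for stopping is given, and any count of progressors would include some who start new therapy or die before day 90.

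**Conclusion.** The point holds for subjects who stop for confirmed progression, or progress in follow-up before day 90, and have not started new therapy. For those who stop for progression, 53 to 67 of the 90 days (59-74%) rest on passive reporting. Those who progress in follow-up lose whatever remains after their last review. Subjects who start new therapy before day 30 have only the stretch from the brought-forward visit to day 30, unless the later ECI paragraph governs. The day counts assume that the safety visit takes place within its window and that no unscheduled contact asks about events. The number of subjects affected and the number of SAEs missed cannot be derived from the documents. This is a cheap improvement to the completeness of a primary safety objective, not a flaw that invalidates the safety analysis.

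**What to change.** - **Flow charts 6.1 and 6.2:** mark adverse event review under Survival Follow-up, restricted to SAEs and ECIs and to the time while the reporting window is open.
- **Section 7.1.5.4.3:** state that a subject who enters survival follow-up before day 90 without new therapy has a call at day 90 (+7) after the last dose that asks about SAEs and ECIs since the last contact. It should not apply to everyone in survival follow-up: a subject who progresses later enters after day 90, and one on new therapy has a shorter window under section 7.2.3.1.
- **Brought-forward safety visits:** where the visit is moved earlier for new therapy, add one adverse event question by telephone at day 30.
- **Section 7.2.3.2:** reconcile the two statements on whether the ECI window ends 30 days after treatment stops or 30 days after new therapy starts.

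The cost is small. If the 12 weeks run from the last dose, the existing call moves from day 84 to day 90, a shift of 6 days. If they run from a day-30 visit, it moves from day 114 to day 90, which is 24 days earlier, or becomes one additional short call. The day-30 question is also one short call. Reported late-SAE counts may rise slightly. Treatment is unchanged.
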